3 OBJECTIVES AND ENDPOINTS

3.1 OBJECTIVES AND ENDPOINTS

All endpoints will be assessed independently for each biomarker-defined cohort. **Tables A and B** list the objectives and endpoints for this study. Cohorts are stratified based on disease

The information contained in this protocol and all other information relevant to this study are confidential and proprietary information of Strata Oncology Inc., except as may be required by federal, state or local laws or regulation, and may not be disclosed to others without prior written permission of Strata.

Page 19 of 56

severity: (1) traditionally defined metastatic/advanced (tdMeta), and (2) micro-metastatic (μ Meta).

Table A: StrataPATH Objectives and Endpoints for tdMeta Cohorts

tdMeta Cohorts	
OBJECTIVES	ENDPOINTS
Primary	
Assess the clinical activity of anti-cancer therapies in participants with pre-specified biomarker profiles.	ORR – Overall Response Rate is defined as the percentage of participants with a best overall response of CR or PR based on Response Evaluation Criteria in Solid Tumors (RECIST) 1.1, as assessed by the investigator.
Secondary	
Assess the duration of response in anti-cancer therapies in participants with pre-specified biomarker profiles.	
 DoR – Duration of response is defined as the time from first documentation of disease response (CR or PR) until first documentation of progressive disease. TTD – Time to treatment discontinuation is defined as length of time from the date the participant initiates the systemic treatment to the date the participant discontinues treatment TTnT – Time to next treatment is defined as the length of time from the date the participant initiates study treatment to the date the participant initiates their next systemic treatment or death.
Evaluate ctDNA response rate at timepoints for participants who received anti-cancer therapies with pre-specified biomarker profiles.	ctDNA response – Proportion of participants with a <50% ratio of mean VAF will be defined as ctDNA responders. Molecular response is calculated as a ratio of mean VAF on-treatment at different timepoints compared to their baseline VAF.
Evaluate overall survival (OS) for participants who received an anticancer therapy with pre-specified biomarker profiles.	OS – Time from initiation of treatment until death from any cause.
Monitor and characterize the overall safety in the biomarker cohorts	The incidence of serious adverse events (SAEs).
Exploratory	
Explore the relationship between serial ctDNA measurement and participant response to therapy.	N/A

Table B: StrataPATH Objectives and Endpoints for μ Meta Cohorts

μ Meta Cohorts

The information contained in this protocol and all other information relevant to this study are confidential and proprietary information of Strata Oncology Inc., except as may be required by federal, state or local laws or regulation, and may not be disclosed to others without prior written permission of Strata.

Page 20 of 56

OBJECTIVES	ENDPOINTS
Primary	
Evaluate ctDNA response rate at 6 months for participants who received an anticancer biomarker-guided therapy.	ctDNA response – Proportion of participants with a <50% ratio of mean VAF will be defined as ctDNA responders. Molecular response is calculated as a ratio of mean VAF on-treatment at 6 months compared to their baseline VAF.
Secondary	
Evaluate the ctDNA response rate at additional timepoints for participants who receive an anticancer biomarker therapy.	ctDNA response – Proportion of participants with a <50% ratio of mean VAF will be defined as ctDNA responders. Molecular response is calculated as a ratio of mean VAF on-treatment at additional timepoints compared to their baseline VAF.
Evaluate Disease-Free Survival (DFS) stratified by ctDNA status or response at different timepoints.	DFS – Time from initiation of treatment until disease recurrence or death from any cause.
Assess the correlation between ctDNA and Disease-Free Survival (DFS).	DFS – Time from initiation of treatment until disease recurrence or death from any cause.
Evaluate overall survival (OS) for participants who received an anticancer biomarker-guided therapy.	OS – Time from initiation of treatment until death from any cause.
Monitor and characterize the overall safety for participants in the biomarker cohorts	Incidence of serious adverse events (SAEs).

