4 STUDY DESIGN

4.1 OVERALL DESIGN

Participants who are 18 years of age or older, have been diagnosed with histologically documented solid tumors, have an eligible biomarker profile, and are planned for treatment may be eligible for this study according to the criteria in **Sections 5.1-5.2** and the supplemental criteria in the specific biomarker/drug cohort appendix.

Each biomarker/drug cohort will be described in an appendix to this study protocol. Appendix information includes investigational product overview, rationale for biomarker/drug combination, additional cohort-specific eligibility criteria, study treatment including dosing and administration guidelines, along with known adverse reactions.

After obtaining informed consent, study staff shall assess individual participant eligibility using the criteria in **Sections 5.1-5.2** and the supplemental criteria in the specific appendix they are targeting for enrollment. The designated study staff will enter the participant's details into the electronic data capture (EDC) to support a sponsor-required confirmation of biomarker eligibility. Upon confirmation of eligibility and informed consent procedures, the participant will be formally enrolled into the study. Participants will be treated with the applicable cohort's study drug according to dosing instructions in the approved product labeling or provided Investigator's Brochure (IB).

For participants who exhibit more than 1 eligible biomarker result, the treating physician should determine the most appropriate cohort assignment. Factors for consideration include the drug's dosing and administration guidelines, as well as the commercially available product prescribing instructions or provided IB.

A leftover tumor specimen (if historical comprehensive genomic profiling (CGP) and/or ribonucleic acid (RNA) profiling results are not available for submission) and blood sample for ctDNA analysis will be collected at study entry (prior to therapy start). Blood samples will be

The information contained in this protocol and all other information relevant to this study are confidential and proprietary information of Strata Oncology Inc., except as may be required by federal, state or local laws or regulation, and may not be disclosed to others without prior written permission of Strata.

Page 23 of 56

collected and CT/MRI scans will be performed until treatment discontinuation as outlined in the Study Schedule of Activities (SOA) (**Section 7.2**).

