5.7 PARTICIPANT DISCONTINUATION/WITHDRAWAL FROM THE STUDY

Participants are free to withdraw from participation in the study at any time upon request.

An investigator may discontinue or withdraw a participant from the study for any of the following reasons:

- Pregnancy.
- Significant study intervention non-compliance.
- If any clinical AE, laboratory abnormality, or other medical condition or situation occurs such that continued participation in the study would not be in the best interest of the participant.
- Disease progression which requires discontinuation of the study intervention.
- If the participant meets an exclusion criterion (either newly developed or not previously recognized) that precludes further study participation.
- Participant unable to receive therapy for greater than 2 weeks.
- Death.

The reason for participant discontinuation or withdrawal from the study will be recorded on the CRF. Participants who sign the ICF but do not receive the study intervention may be replaced. Participants who sign the ICF, receive the study intervention, and subsequently withdraw, or are withdrawn or discontinued from the study, will be replaced if the reason for withdrawal is not due to failure to respond. Any participants who withdraw due to progression will be counted in efficacy calculations. Any participant withdrawal and replacement will be detailed in the Screening and Enrollment Log.

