6.4 STUDY AGENT DISCONTINUATION

Discontinuation of dosing does not mean discontinuation from the study. Remaining study procedures should be completed as indicated by the study protocol regardless of whether the participant is on active treatment. If a clinically significant finding is identified (including, but not limited to, changes from baseline) after enrollment, the investigator or qualified designee will determine if any change in study drug administration is needed. Any new, clinically relevant finding that is both unexpected and thought to be related to the drug will be reported as an SAE under Other Medically Important Event as described in Section 8.2.2. All AEs and SAEs will be reported and captured in the CRF.

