7 STUDY PROCEDURES AND SCHEDULE

7.1 STUDY PROCEDURES

7.1.1 STUDY SPECIFIC PROCEDURES

All procedures listed here are specific to the study and are not part of standard clinical care:

- Review and sign informed consent
- Eligibility criteria review
- Biological specimen collection
 - Two 10 milliliter (mL) tube of blood (20 mL total) will be collected via venipuncture
- Archival FFPE tissue submission (if historical CGP and/or Strata RNA profiling results are unavailable or as otherwise indicated within the cohort-specific criteria)
- Biomarker confirmation (biomarker test results)
- Data collection of any standard of care procedures conducted as part of regular clinical visits
- Study drug dispensing
- Study drug administration
- CT/MRI scan of abdomen, chest, and pelvic area
- Tumor assessments (RECIST 1.1 or iRECIST)
- Drug administration and accountability
- Evaluation and documentation of adverse events (AEs) or serious adverse events (SAEs)
- Electrocardiograms (EKGs) and/or echocardiogram (Echo) are required for eligibility determination at screening. If not done as part of standard of care work-up or historical

The information contained in this protocol and all other information relevant to this study are confidential and proprietary information of Strata Oncology Inc., except as may be required by federal, state or local laws or regulation, and may not be disclosed to others without prior written permission of Strata.

Page 30 of 56

EKG and/or Echo are not available, these tests should be performed as research procedures.

- A serum pregnancy test is required if the pre-treatment urine pregnancy test is positive or inconclusive. Pregnancy tests must be documented as negative within 3 days of study treatment.

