7.2.3.4 POST-TREATMENT

Study drug will be discontinued upon disease progression or based on physician's discretion as described in **Section 5.5**. Site staff should collect unused study drug and any empty packaging and perform drug accountability upon study drug discontinuation. Participants that discontinue drug will remain on study for 3 years from the date of informed consent for follow-up data entry purposes only. No additional study specific procedures will occur following discontinuation. Participants will continue to see their physician for SOC clinic visits. Site staff will be responsible

The information contained in this protocol and all other information relevant to this study are confidential and proprietary information of Strata Oncology Inc., except as may be required by federal, state or local laws or regulation, and may not be disclosed to others without prior written permission of Strata.

Page 37 of 56

for collecting and entering the information below in EDC from the participants SOC clinic visits every 3 months.

- Medical history (specifically, disease recurrence and/or survival status)
- Concomitant medications (specifically, anticancer therapies)
- Standard of care procedures, including ECOG status

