9 STATISTICAL CONSIDERATIONS

9.1 SAMPLE SIZE DETERMINATION

The information contained in this protocol and all other information relevant to this study are confidential and proprietary information of Strata Oncology Inc., except as may be required by federal, state or local laws or regulation, and may not be disclosed to others without prior written permission of Strata.

Page 45 of 56

The study design is similar to a basket trial with each basket molecularly defined. For both cohorts (tdMeta and μ Meta), sample size calculations were completed under the following assumptions:

- Each cohort will enroll unique participants. Although participants may qualify for enrollment in more than one cohort, they will be enrolled in only one biomarker cohort (Refer to Section 10.2 for definitions).
- Each molecularly defined cohort will be evaluated independently.
- tdMeta and μ Meta cohorts will be evaluated independently.

Sample size was determined using a two-stage design based on minimizing the risk of a false negative result. The binomial probability of observing an exact number of responses was used similar to that in a Simon's two-stage design.^{19,20} The null hypothesis that the true response rate is 0.05 will be tested against a one-sided alternative. In the first stage, 12 patients will be accrued per cohort. If there are 1 or fewer responses in these 12 patients, the study will be stopped for that cohort. Response will be defined as partial response or complete response for tdMeta cohorts and <50% ctDNA mean VAF ratio for μ Meta cohorts. Otherwise, 23 additional patients will be accrued for a total of 35. The null hypothesis will be rejected if 6 or more responses are observed in 35 patients. This design yields a type I error rate of 0.001 and a power of 88% when the true response rate is 0.30.

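### μMeta primary endpoint: the protocol conflicts on whether the 6-month ctDNA sample is taken after drug stops, and its replacement rule lets early stoppers leave the 12 and the 35 selectively

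*Protocol*

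**What the plan says.** **Endpoint.** Protocol 3.1, Table B defines the μMeta primary endpoint as the proportion of participants whose mean VAF ratio is below 50%: "Molecular response is calculated as a ratio of mean VAF on-treatment at 6 months compared to their baseline VAF". Section 3.2.2 gives the same 6-month timing.

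**Draws end with drug.** Section 4.1 says blood samples will be "collected and CT/MRI scans will be performed until treatment discontinuation". Table D marks whole blood at baseline and on treatment only (every 8 weeks, ±2, in year 1, plus one draw at progression) and leaves the post-treatment column empty. Section 7.2.3.4 adds: "No additional study specific procedures will occur following discontinuation". Blood collection is such a procedure: it is in the 7.1.1 list, which opens "All procedures listed here are specific to the study and are not part of standard clinical care".

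**Procedures continue after drug.** Section 6.4: "Remaining study procedures should be completed as indicated by the study protocol regardless of whether the participant is on active treatment".

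**Who is counted.** Section 5.7 says treated participants who withdraw or are discontinued from the study "will be replaced if the reason for withdrawal is not due to failure to respond". It also says: "Any participants who withdraw due to progression will be counted in efficacy calculations". Sections 9.1 and 9.3.6 stop a cohort at 1 or fewer responses in 12; 9.1 rejects the null at 6 or more in 35. Section 9.1 defines response there as "<50% ctDNA mean VAF ratio for μ Meta cohorts", with no timepoint.

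**The concern.** Table D lets drug stop at progression or at the physician's discretion, so stopping before month 6 is foreseeable. Two sites can then follow the protocol faithfully and differ: one takes no 6-month sample and the other does. If taken, the sample is not on-treatment, so it does not meet Table B either.

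The absent values will not be a random subset, because they follow toxicity, participant choice and recurrence. Section 5.7 adds a second selection step. A treated participant withdrawn for toxicity or choice is replaced, so the 12 and the 35 can fill up with people who tolerated and stayed on drug. Because 9.1 and 9.3.6 do not repeat the timepoint, an earlier draw could also be put forward as the response for someone who stopped.

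At stake are the go/no-go count and the primary estimate of each μMeta cohort. A statistical analysis plan can assign a status to a missing value, but it cannot supply blood that was never drawn.

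**Working it through.** **1. Which draw serves month 6.** Eight-weekly draws fall at weeks 8, 16, 24 and 32. With ±2 weeks, the windows are 6–10, 14–18, 22–26 and 30–34. Six months is about 26 weeks, so the week-24 draw (22–26) is the nearest. A participant who stops before about week 22 has no on-treatment draw in that window.

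**2. What each passage gives that participant.**

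| Passage | 6-month sample? | Meets Table B? |
|---|---|---|
| 4.1, Table D, 7.2.3.4 | No | No value exists |
| 6.4, read as continuing draws | Yes | No, off treatment |
| 6.4, read as deferring to Table D | No | No value exists |
| Table D, draw at progression | At progression only | No, not at 6 months |

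**3. Operating characteristics of the written rule.** Inputs from 9.1: 12 then 35 participants, continue with at least 2 responses, reject with at least 6, null rate 0.05, alternative 0.30. The exact probability of rejection is

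P(p) = Σ (x = 2 to 12) Bin(x; 12, p) × Pr[Bin(23, p) ≥ max(0, 6 − x)].

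This gives P(0.05) = 0.0052 and P(0.30) = 90.1%. Section 9.1 states 0.001 and 88%, which the written rule does not reproduce. A final cut-off of 7 or more gives 0.0012 and 87.5%, close to the stated pair. That mismatch is a separate matter; the rule is used here as written.

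**4. Effect of early stopping.** Let d be the share stopping before month 6. The protocol gives no such rate for μMeta, so d = 5% to 20% is an assumption. Two treatments of the stoppers are compared:

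- *Counted as non-responders, stopping independent of response:* the effective rate is p(1 − d). At d = 20%: 0.30 × 0.80 = 0.24.
- *Replaced, and would not have responded:* the effective rate is p/(1 − d). At d = 20%: 0.05/0.80 = 0.0625.

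| d | Expected stoppers of 35 | Counted: effective rate at 0.30 | Counted: power | Replaced: effective rate at 0.05 | Replaced: P(reject) |
|---|---|---|---|---|---|
| 0 | 0 | 0.300 | 90.1% | 0.0500 | 0.0052 |
| 5% | 1.75 | 0.285 | 87.7% | 0.0526 | 0.0066 |
| 10% | 3.5 | 0.270 | 84.6% | 0.0556 | 0.0085 |
| 20% | 7 | 0.240 | 76.4% | 0.0625 | 0.0145 |

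In the counted case, the chance of stopping at 12 when the true rate is 0.30 rises from 8.5% (d = 0) to 10.3% (5%) and 17.8% (20%).

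**The case against.** The other side has several fair points.

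- **Section 6.4 may not conflict.** It is qualified by reference back to the protocol, so it can be read as deferring to Table D. A reader might infer that 6.4 already requires the post-discontinuation draws; with that qualifier, the text does not support so firm a reading. But on the deferring reading the clause about active treatment has no effect on blood draws, and early stoppers certainly lack the sample.
- **The timepoint is stated.** A reader might infer from 9.1 and 9.3.6 that μMeta response has no timepoint at all. Table B and 3.2.2 both give 6 months. The gap is only that the decision rule does not repeat it.
- **Missing data belong to the analysis plan.** Section 9.3.1 says so, and that stands for imputation methods. Sampling, replacement and the stopping counts, however, are fixed in this protocol.
- **An on-treatment endpoint is legitimate.** A reader might conclude that the word on-treatment in Table B is a mistake. It is a choice of estimand, and with stoppers scored as non-responders it needs no later sample.
- **Section 5.7 may not reach people who only stop dosing.** Section 6.4 separates stopping drug from leaving the study, and 5.7 counts progression withdrawals. This limits the replacement path to those treated as withdrawn for other reasons; it does not close it. Nor does 5.7 say what status a progression withdrawal receives.
- **Dropping without replacement leaves the decision unchanged.** Removing non-responders alters the estimate but not the count compared with 6. The false-positive effect needs replacement.

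It is also tempting to take the 14% in section 2.3 as the early-stop rate and argue that 10 responders in 35 could be reported as anything from 5/35 (14%) to 10/30 (33%). The documents do not support this. The 14% is adverse-event discontinuation of adjuvant pembrolizumab in one melanoma trial and is not tied to month 6. The two ends also assume opposite things about the same five people.

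Finally, section 2.3 says only that the study may include μMeta cohorts, and the cohort appendices are not shown, so nothing visible establishes that one is open.

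**Conclusion.** The point holds as a conflict between passages combined with a denominator that can shift. No reading of the text gives an early stopper the outcome Table B defines, and 5.7 allows some of them to be replaced in the counts that decide the cohort.

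Over an assumed early-stop share of 5% to 20%, counting stoppers as non-responders costs between 2.4 and 13.7 percentage points of power at 0.30 (90.1% to 87.7% or 76.4%). Replacement takes rejection at 0.05 from 0.0052 to between 0.0066 and 0.0145, about 1.3 to 2.8 times as high, though still small in absolute terms.

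These figures rest on the assumed range and on two simplifications: stopping independent of response in the first case, and every replaced stopper a non-responder in the second. Stoppers who would have responded would weaken or reverse the second effect. The textual conflict does not depend on any of these assumptions.

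**What to change.** 1. Reconcile 6.4 with 4.1, Table D and 7.2.3.4, so that one rule states whether the week-24 (±2) ctDNA sample is taken after drug stops. Make the on-treatment wording in Table B and 3.2.2 match that rule, whichever way it is settled.
2. State in 9.1 and 9.3.6 that μMeta response means the 6-month ratio of Table B.
3. State that every dosed participant stays in the 12 and the 35, and that replacement under 5.7 does not remove anyone from the primary analysis. Participants with recurrence, death, new anticancer therapy or no valid sample before the 6-month assessment count as non-responders.

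Naming new anticancer therapy prevents a later drug's effect from being credited to the study drug if draws continue.

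**Cost.** Protocol wording, and a slightly lower reported response rate. If draws continue after drug stops, a few two-tube blood draws in early stoppers. If they do not, every early stopper is a non-responder, and the power loss shown above should be accepted openly. Samples missed during accrual cannot be recovered, so this should be settled before μMeta participants are enrolled.

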This study may also include separate cohorts of patients in the micro-metastatic setting (as defined by ctDNA positive liquid biopsy) post-standard of care adjuvant therapy, but not yet having been identified as traditionally advanced or metastatic using standard of care imaging or biochemical testing. All therapies are FDA-approved in oncology with demonstrated safety profiles in the traditionally advanced setting; the toxicity profile may be different in the micro-metastatic setting. The utility of targeted therapy in the early-stage setting has been demonstrated with the approval of osimertinib for patients with EGFR-mutated NSCLC. The ADAURA trial demonstrated that osimertinib was well tolerated post-resection in patients with stage IB-III NSCLC; dose reductions due to adverse events occurred in 9% of patients in the treatment group.⁶ This was comparable to the 10% dose reduction rate observed in first-line patients with advanced NSCLC at the same recommended dose.⁷ Comparatively, the toxicity profile of immunotherapies in early-stage disease may not be as favorable. Dose discontinuation due to adverse events occurred in only 9% of patients with advanced melanoma treated with pembrolizumab in KEYNOTE-001, while 14% of melanoma patients that received pembrolizumab as adjuvant therapy post resection in KEYNOTE-054 experienced adverse event related dose discontinuation.^{8,9} Recently announced data from KEYNOTE-564, however, suggests that the toxicity profile of pembrolizumab when used as adjuvant therapy in patients with renal cell carcinoma following nephrectomy was consistent with previously reported studies with the anti-PD-1 therapy.¹⁰ To monitor risk and capture any differences in toxicity profiles between patient populations, full safety data collection will be collected in this study.

More information on the clinical data associated with each therapeutic study arm and known and expected benefits, risks, and reasonably expected adverse events (Aes) may be found in the corresponding appendices.

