3.2.3 DISEASE-FREE SURVIVAL

Disease-free survival (DFS) is defined as the time from date of first dose until disease recurrence or death from any cause. The most frequent use of this endpoint is in the adjuvant setting after definitive surgery or radiotherapy and is a recommended clinical endpoint based on FDA's guidance Clinical Trial Endpoints for the Approval of Cancer Drugs and Biologics.¹¹

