7.2.3.3 ON TREATMENT

- Review of medications
- Negative pregnancy test (urine or serum)
- Obtain two 10 mL tubes of whole blood and complete research blood collection form every 8 weeks during the first year of treatment and every 12 weeks thereafter and once upon disease progression
 - Complete research blood collection form
- Dispense study drug
- Administer study drug and/or review administration instructions with participant
- Perform drug accountability
- Enter data from any standard of care procedures in the EDC, including ECOG status
- Document any AEs or SAEs

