9.3 STATISTICAL ANALYSES

9.3.1 GENERAL APPROACH

This study will use an adaptive approach, with on-treatment data guiding trial adaptation and success or futility of each cohort. All statistical analyses will be pre-specified and finalized for each cohort prior to database lock. The statistical analysis plan (SAP) will describe the study populations to be included in the analyses and the procedures for accounting for missing, unused, and spurious data. High-level methods are described here.

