9.3.2 EFFICACY ANALYSES

Efficacy analyses for ORR and DoR are based on the responses from Investigator-recorded measurements and assessments for target, nontarget, and new lesions according to RECIST 1.1.²¹

- ORR is defined as the percentage of participants with a best overall response of complete response (CR) or partial response (PR).
- DoR is defined as the time from first documentation of disease response (CR or PR) until first documentation of progressive disease.

Efficacy analyses for ctDNA response rate will be based on the proportion of participants considered responders compared to non-responder participants. Responders are defined as any participant with <50% ratio of mean VAF.

ORR and ctDNA response rate will be estimated by the proportion of participants with objective response and ctDNA response respectively and their 95% confidence intervals will be estimated using the exact binomial method. Other time-to-event efficacy analyses including TTD, TTNT, DFS and OS will be summarized using the Kaplan-Meier method with the appropriate time-defined cut-offs.

Additional supportive analyses of efficacy endpoints may be conducted using iRECIST.²²

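### The DFS that Table B splits by later ctDNA results is timed from first dose, with only Kaplan-Meier named; curves drawn that way contain immortal time

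*Protocol*

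**What the plan says.** - **Grouping.** Protocol section 3.1, Table B, lists the μMeta secondary objective "Evaluate Disease-Free Survival (DFS) stratified by ctDNA status or response at different timepoints". The synopsis carries the same objective, with status only.
- **Time origin.** The endpoint cell in that row defines DFS as "Time from initiation of treatment until disease recurrence or death from any cause". Section 3.2.3 agrees: "the time from date of first dose until disease recurrence or death from any cause".
- **Method.** Section 9.3.2, in one sentence that also covers TTD and TTNT, says "DFS and OS will be summarized using the Kaplan-Meier method with the appropriate time-defined cut-offs".
- **Entry status.** Section 2.3 describes the micro-metastatic setting "as defined by ctDNA positive liquid biopsy".
- **Draws.** Section 7.2.3.3 takes blood "every 8 weeks during the first year of treatment and every 12 weeks thereafter and once upon disease progression". Section 7.2.3.4 adds "No additional study specific procedures will occur following discontinuation", and study drug stops at progression.
- **Left to the SAP.** Section 9.3.1 assigns to it "the study populations to be included in the analyses and the procedures for accounting for missing, unused, and spurious data".

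**The concern.** Because all μMeta participants are ctDNA-positive at entry, baseline status cannot separate them. The strata come into being at a later draw, and only for people still on study and sampled then. The clock, however, starts at first dose. Between first dose and the draw, a participant who ends up in a stratum cannot have had a DFS event. Kaplan-Meier curves that count this stretch as time at risk contain immortal time.

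A participant who recurs before the draw has no scheduled result for it, and each simple way of handling such participants has a cost:

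- Left out: both curves sit at 100% until the draw, and DFS from first dose is too high in both groups.
- Counted as non-responders: all early events fall in one group.
- Classified from the progression draw: the group is defined at the DFS event itself.

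The study has no control arm, so stratified DFS levels are likely to be read directly. Section 3.2 also presents ctDNA response as a potential surrogate, which makes any artefact linking it to DFS unwelcome.

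**Working it through.** The protocol gives no DFS median, rate or hazard ratio, so there is no plan figure to reproduce. What follows is an illustration.

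**Inputs from the protocol.** Draws every 8 weeks in year 1 (week 8 = 1.84 months, week 16 = 3.68 months); month 6 as the primary ctDNA timepoint; follow-up to 36 months; 35 participants in a full cohort.

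**Assumptions, not in the protocol.** Exponential DFS, S(t) = 0.5^(t/m), with median m = 12 months (range 9 to 24); ctDNA response unrelated to DFS; 40% response among those recurrence-free at the draw; everyone recurrence-free is sampled.

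**(a) Earlier recurrences left out.** Both curves from first dose show S(t)/S(L) after a draw at time L, instead of S(t). For m = 12, the true S(12) is 0.500.

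| Split at | S(L) | 12-month DFS shown, m = 12 | Overstatement, medians 24 to 9 months | Recurrence-free of 35, m = 12 |
|---|---|---|---|---|
| Week 8 | 0.899 | 0.500/0.899 = 0.556 | 4 to 6 points | 31.5 |
| Week 16 | 0.809 | 0.500/0.809 = 0.618 | 8 to 13 points | 28.3 |
| Month 6 | 0.707 | 0.500/0.707 = 0.707 | 13 to 23 points | 24.7 |

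The same factor applies to both groups, so the ratio between them stays at 1.0.

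**(b) Earlier recurrences counted as non-responders** (a rule the protocol does not state). Take m = 12, L = 6, hazard λ = ln 2/12 = 0.05776 per month, S(36) = 0.125, and work per participant enrolled.

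- Responders: events 0.4 × (0.7071 − 0.125) = 0.2328. Person-months 0.4 × [6 × 0.7071 + (0.7071 − 0.125)/0.05776] = 5.728. Rate 0.04065.
- Non-responders: events 0.875 − 0.2328 = 0.6422. Person-months 0.875/0.05776 − 5.728 = 9.420. Rate 0.06817.
- Rate ratio 0.04065/0.06817 = 0.596, where the truth is 1.

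The same calculation gives 0.71 at week 16 and 0.83 at week 8. Over medians of 9 to 24 months the ratio is 0.55 to 0.67 at month 6, 0.67 to 0.78 at week 16 and 0.80 to 0.88 at week 8.

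**(c) Landmark check.** In simulations of 20,000 participants with no true effect (medians 6, 12, 18 and 24 months; response 30% or 50%), rule (b) at month 6 gave hazard ratios of 0.55 to 0.63 at a 12-month median. Restricting to those recurrence-free at month 6 and restarting the clock there gave 0.97 to 1.02 in all eight scenarios.

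**The case against.** The strongest reply is that no sentence in the protocol orders Kaplan-Meier curves from first dose split at a later draw. Table B gives an objective and a definition but no method. Kaplan-Meier comes from the general sentence in section 9.3.2, which unstratified curves would satisfy. Section 9.3.1 calls its methods high-level and leaves populations and missing data to the SAP, which could adopt a landmark. A first-dose origin is ordinary for DFS and is compatible with ctDNA as a time-dependent covariate.

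Much of this stands: the problem appears only when the two sections are read together, and the SAP could prevent it. But the origin and the post-baseline strata are fixed in the same Table B row, and neither is among the items section 9.3.1 defers. A landmark in the SAP would have to depart from the stated origin. The reference to time-defined cut-offs in section 9.3.2 names no landmark and does not move the origin.

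It is also fair to say that the landmark excludes the same early recurrences as case (a), and that its curve also reads 71% six months after a month-6 landmark. The difference is what the number claims: correctly, DFS among those who reached month 6, rather than DFS from first dose.

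Section 6.4 says remaining study procedures continue off treatment, which sits uneasily with section 7.2.3.4. The latter is the more specific text, and a draw taken after recurrence would still classify the participant after the event.

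**Conclusion.** The point holds in limited form. Followed as written, Table B and section 9.3.2 together lead to curves with immortal time. The direction of the overstatement in case (a) does not depend on the assumptions; its size does. At an assumed 12-month median, 12-month DFS is overstated by about 6 points for a week-8 split and 21 points for a month-6 split.

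Two stronger readings are tempting, and the documents support neither:

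- *That the plan builds in a false advantage for ctDNA responders.* This needs early recurrences to be counted as non-responders or classified from the progression draw. The protocol states neither rule. If they are simply left out, the contrast stays fair.
- *That the separate objective on the correlation between ctDNA and DFS is also wrong.* No method is stated for it, so there is nothing there to be in error.

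The reach is one secondary objective, with no planned DFS test, in cohorts that section 2.3 says the study may include. The primary ctDNA response rate, the stage-1 stopping rule and unstratified DFS are unaffected.

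**What to change.** In Table B and section 9.3.2, state: *DFS by ctDNA status or response at a given timepoint is a landmark analysis of participants who are alive, recurrence-free and sampled at that draw, with time measured from the landmark. The draw taken at progression is not used for classification. Kaplan-Meier DFS from first dose is reported unstratified.* For consistency, the ctDNA-DFS correlation can use the same landmark, or a Cox model with ctDNA as a time-dependent covariate, which may keep the first-dose origin.

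The change is wording only and uses data already collected. Its cost is that participants who recur or stop drug before the landmark do not inform the stratified comparison. At an assumed 12-month median about 25 of 35 remain at month 6 (22 to 29 for medians of 9 to 24 months), 28 at week 16 and 31 at week 8, and fewer if some stop drug early.
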